9.8 Premature termination of the study

There are no predefined criteria for premature termination of the study. If, however, during the conductance of the study information becomes available showing that continuation of the study would result in a significant safety risk for the patients, the principal investigator and project leader will decide to terminate the study.

10. SAFETY REPORTING

10.1 Section 10 WMO event

In accordance to section 10, subsection 1, of the WMO, the investigator will inform the subjects and the reviewing accredited medical ethics committee if anything occurs, on the basis of which it appears that the disadvantages of participation may be significantly greater than was foreseen in the research proposal. The study will be suspended pending further review by the accredited medical ethics committee, except insofar as suspension would jeopardize the subjects' health.

The investigator will take care that all subjects are kept informed.

10.2 AEs and SAEs

10.2.1 Adverse events (AEs)

An adverse event is any untoward medical occurrence in a patient administered a medicinal product and which does not necessarily have to have a causal relationship with this treatment. An adverse event can therefore be any unfavorable and unintended sign (for example, an abnormal laboratory finding), symptom, or disease temporally associated with the use of a medicinal product, whether or not considered related to this medicinal product. (ICH E2D).

10.2.2 Serious adverse events (SAEs)

A serious adverse event is any untoward medical occurrence or effect that at any dose:

- results in death;
- is life threatening (defined as an event in which the subject was at risk of death at the time of the event; it does not refer to an event which hypothetically might have caused death if it were more severe;
- requires hospitalisation or prolongation of existing inpatients' hospitalisation;
- results in persistent or significant disability or incapacity;
- is a congenital anomaly or birth defect;

- is an important medical event (defined as a medical event(s) that may not be immediately lifethreatening or result in death or hospitalization but, based upon appropriate medical and scientific judgment, may jeopardize the subject or may require intervention [eg, medical, surgical] to prevent one of the other serious outcomes listed in the definition above). Examples of such events include, but are not limited to, intensive treatment in an emergency room or at home for allergic bronchospasm; blood dyscrasias or convulsions that do not result in hospitalization.)

AEs will be recorded in the electronic case report form (eCRF).

10.2.3 Adverse events of interest

Urinary tract infections

Genital infections

Diabetic ketoacidosis (DKA)

Volume depletion (Eg, dehydration, hypovolemia, or hypotension)

Fractures

Major hypoglycaemic event

A major hypoglycaemic event is defined as an event that requires assistance of another person to actively administer carbohydrates, glucagon, or take other corrective actions. Plasma glucose concentrations may not be available during an event, but neurological recovery following the corrective actions is considered sufficient evidence that the event was induced by a low plasma glucose concentration.

Acute Kidney Injury

Acute kidney injury is defined as an increase of 40% in serum creatinine from the previous visit or hospitalization due to acute kidney injury.

Amputation:

Amputations will be recorded in the eCRF. We will report the underlying cause of amputation as the AE and include the information regarding the actual amputation in the AE description rather than reporting the amputation procedure as a separate AE.

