which in turn leads to vasodilation of the afferent arteriole and hyperfiltration³⁸. SGLT2i increases delivery of sodium to the macula densa, restores TGF and results in vasoconstriction of the afferent arteriole, leading to reductions in intraglomerular hypertension, glomerular filtration rate (GFR) and albuminuria³⁹. These mechanisms appear to be intact in non-DM populations as well. Bay and colleagues determined the effect of canagliflozin versus placebo on 376 non-diabetic obese subjects for 12 weeks ⁴⁰. Canagliflozin reduced weight and blood pressure over the study period. A decrease in eGFR over the 12-week period was observed with canagliflozin, consistent with SGLT2 inhibition-mediated reductions in glomerular pressure. Our group also published results of the DIAMOND trial where fifty-three participants with non-diabetic CKD, eGFR \geq 25ml/min/1.73m², and proteinuria \geq 500 to \leq 3500mg/day were treated with dapagliflozin and placebo in a randomized, double-blind 6-week crossover trial. Dapagliflozin resulted in an acute and reversible decline in measured GFR while decreasing body weight and increasing markers of hemoconcentration, suggesting mechanisms of kidney function are intact irrespective of glycemic effects⁴¹. These mechanisms are shown in Figure 1. The natriuresis induced by SGLT2i is also one of the postulated mechanisms underlying reductions in the systolic and diastolic blood pressure and arterial stiffness observed with SGLT2i^{42, 43, 28, 44}. Decreases in systemic and intraglomerular hypertension with SGLT2i may in turn be responsible for decreases in albuminuria and CKD progression in clinical trials of patients with and without T2D^{28, 45}. Interestingly, although there is an attenuation of the glucose lowering effects of SGLT2i as GFR declines due to reduced glucosuria, natriuresis-related reductions in blood pressure and reductions in albuminuria persist even in the setting of reduced kidney function⁴⁶. From a cardiac perspective, it is hypothesized that the natriuresis-induced decrease in intravascular volume and reduction in arterial stiffness that occurs with SGLT2i leads to an unloading of the myocardium and an improvement in cardiac function, although other factors may also play a role^{39, 47}.

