3.3 Anticipated Outcomes

- 1. We hypothesize that dapagliflozin will result in a significant reduction in systolic and diastolic blood pressure in a cohort of KTR with or without T2D and PTDM.
- 2. We hypothesize that dapagliflozin will be well tolerated in KTR with or without T2D and PTDM, with adverse events similar to that of non-transplant populations. We also hypothesize that there will be no clinically significant changes in CNI levels or episodes of acute rejection in KTR treated with dapagliflozin vs. placebo during the study.
- 3. We hypothesize that dapagliflozin will result in a significant natriuresis, as well as reductions in arterial stiffness, albuminuria, allograft hypoxia and markers of oxidative stress, while having neutral effects on cardiac and renal function over the course of the 12-week study period.
- 4. We hypothesize that the glucose-lowering effects of dapagliflozin will be modest in KTR with T2D or PTDM due the high prevalence of CKD in this population. In participants without T2D or PTDM, we do not expect any glucose lowering.

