9.5 Reasons for possible drug discontinuation

- 1. Serious adverse events or an intolerable adverse effect such as a persistent allergy or rash;
- 2. Clinically significant persistent changes from baseline based on laboratory safety assessments;
- 3. Pregnancy or breastfeeding;
- 4. Withdrawal of consent;
- 5. Participant unable to adequately complete study visits or procedures.

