severe nausea, but not a SAE unless it meets the criteria shown in above. On the other hand, a stroke that results in only a limited degree of disability may be considered a mild stroke but would be a SAE when it satisfies the above criteria.

• Causality Collection

The Investigator will assess causal relationship between Investigational Product and each SAE/DAE, and answer 'yes' or 'no' to the question 'Do you consider that there is a reasonable possibility that the event may have been caused by the investigational product?'

• Adverse Events Based on Signs and Symptoms

All SAEs/DAEs/AE spontaneously reported by the patient or reported in response to the open question from the study personnel: 'Have you had any health problems since the previous visit/you were last asked?' or revealed by observation will be collected and recorded in the eCRF. When collecting SAEs/DAEs/AEs, the recording of diagnoses is preferred (when possible) to recording a list of signs and symptoms. However, if a diagnosis is known and there are other signs or symptoms that are not generally part of the diagnosis, the diagnosis and each sign or symptom will be recorded separately.

• Adverse Events Based on Examinations and Tests

The results from protocol mandated laboratory tests and vital signs will be summarised in the clinical study report. Deterioration as compared to baseline in protocol-mandated laboratory values, or vital signs should therefore only be reported as AEs if they fulfil any of the SAE criteria, are the reason for discontinuation of study treatment, or fulfil criteria of AEs of special interest. If deterioration in a laboratory value/vital sign is associated with clinical signs and symptoms, the sign or symptom will be reported as an SAE/DAE or AE and the associated laboratory result/vital sign will be considered as additional information. Wherever possible the reporting Investigator uses the clinical, rather than the laboratory term (e.g., anaemia versus low haemoglobin value). In the absence of clinical signs or symptoms, clinically relevant deteriorations in non-mandated parameters should be reported as AE(s).

Any new or aggravated clinically relevant abnormal medical finding at a physical examination as compared with the baseline assessment will be reported as an AE.

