95. [name] DZ, Miller JA, Scholey JW, Bradley TJ, Slorach C, Curtis JR, Dekker MG, Nasrallah R, Hebert RL and Sochett EB. The effect of cyclooxygenase-2 inhibition on renal hemodynamic function in humans with type 1 diabetes. *Diabetes*. 2008;57:688-95.

96. [name] DZ, Sochett EB, Lai V, Dekker MG, Slorach C, Scholey JW and Bradley TJ. Renal hyperfiltration and arterial stiffness in humans with uncomplicated type 1 diabetes. *Diabetes care*. 2010;33:2068-70.

15. Tables and Figures.

Figure 1: Effects of SGLT2 inhibition on the nephron.

Figure reproduced from: van Bommel EJ. Et al. SGLT2 Inhibition in the Diabetic Kidney-From Mechanisms to Clinical Outcome. *Clin J Am Soc Nephrol*. 2017;12:700-710.

[figure not shown]

Figure 2: Potential cardio- and renoprotective mechanisms of SGLT2 inhibition.

Figure reproduced from: Heerspink HJ. et al. Sodium Glucose Cotransporter 2 Inhibitors in the Treatment of Diabetes Mellitus: Cardiovascular and Kidney Effects, Potential Mechanisms, and Clinical Applications. *Circulation*. 2016;134:752-72.

[figure not shown]

Figure 3: Study design

Continuation of existing therapy including immunosuppression, anti-hypertensives, glycemic medications

			1		
SCREENING Visit 1	BASELINE Visit 2 Visit 3	WEEK 1 ACUTE Visit 4	DOSING Visit 5 Visit 6 Visit 7	WEEK 12 CHRONIC Visit 8 Visit 9	Follow UP Visit 10

Observational	Observational studies							
Author, Year	Participants	Design	Treatment	Results				
Rajasekeran et al. Diabetes Care 2017 ¹ Mahling et al.	N=10 KTR & SPKTR with PTDM or T2D N=10 KTR with	Observational cohort study, 80.5 person- months follow- up Observational	canagliflozin	Weight, kg: -2.14 (SD 2.8) Systolic blood pressure, mmHg: -6.5 (SD 10.8) Diastolic blood pressure, mmHg: -4.8 (SD 12) Serum creatinine, mmol/L: 9.7 (SD 14.6); eGFR, mL/min/1.73 ² : -4.3 (SD 12.2) No urinary/mycotic infections, AKI or acute rejection Weight, kg: -1.9 (-1.9 to 0.1)				
Kidney Blood Press Res 2019 ²	PTDM or T2D	study, 6.3 person-years		Systolic blood pressure, mmHg: -2.5 (-36.3 to 0.8) Diastolic blood pressure, mmHg: -0.5 (-9.5 to 7.5) 2 episodes of UTI, 1 episode of AKI				

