# 2. Analysis for secondary objective:

- 2.1. The numbers of hypoglycemic episodes, acute rejection episodes, volume depletion, UTI or genital infection, acute kidney injury, ketoacidosis and serious adverse events will be reported for both the placebo group and dapagliflozin group. No statistical comparisons will be performed.
- 2.2. 2.10. The same models described in the analysis of primary objective 1.1 will be completed for each of the different outcomes.

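### The creatinine criterion for acute kidney injury has no baseline reference, so a rise built up in steps below 40% goes uncounted unless the patient is hospitalised for it

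*Protocol*

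**What the plan says.** Protocol 10.2.3 gives two routes to the event. The first reads: "Acute kidney injury is defined as an increase of 40% in serum creatinine from the previous visit". The second, in the same sentence, is hospitalisation due to AKI. The first looks back one visit; the second needs no creatinine threshold.

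Protocol 10.3 limits when a worsening from baseline in a mandated laboratory value becomes an adverse event. Such changes "should therefore only be reported as AEs if they fulfil any of the SAE criteria, are the reason for discontinuation of study treatment", or meet the criteria for an event of special interest. Associated signs or symptoms are reported in their own right.

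Protocol 9.5 lists "Clinically significant persistent changes from baseline based on laboratory safety assessments" among possible reasons for stopping the drug, without a threshold.

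SAP analysis 2.1 reports by arm "The numbers of hypoglycemic episodes, acute rejection episodes, volume depletion, UTI or genital infection, acute kidney injury" and other events, with no statistical comparison. It gives no AKI definition of its own.

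Table 2 of the Protocol marks blood samples at Visits 1, 3 (baseline), 4 (week 1), 6 (week 6), 9 (week 12) and 10 (week 13). Visits 5, 7 and 8 are phone or e-mail contacts without a blood sample. Protocol 9.1.2 lists day 77, which is Visit 8, as an in-person visit.

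**The concern.** A reference that moves forward at each visit sees only the latest increment. Creatinine that climbs steadily can end far above its starting value without any single step reaching 40%.

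Protocol 10.3 makes this matter more. The special-interest definition is one of only three ways for a laboratory change to become an adverse event, so a rise that misses it, causes no symptoms, meets no seriousness criterion and does not stop treatment leaves no entry in the safety tables.

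Protocol 2.4 names the capture of changes in renal function as part of an important aim, and Protocol 13.6 sets up no data safety monitoring board. The patient-level AKI count therefore carries much of the renal safety evidence. Protocol 2.3 also reports from a non-transplant trial that "Dapagliflozin resulted in an acute and reversible decline in measured GFR", so one should ask what an early rise in creatinine does to the later reference.

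**Working it through.** The plan states no AKI rate or count, so there is no figure to reproduce. The checks use the 40% threshold of Protocol 10.2.3 and the draw schedule of Table 2, reading the previous visit as the previous draw. V3, V4, V6, V9 and V10 denote the visits.

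**1. Stepwise rises.** There are three draws on treatment after baseline: V4, V6 and V9.
- Three steps of 39%: 1.39 × 1.39 × 1.39 = 2.69 times baseline, with no creatinine-defined event.
- Two steps of 20%: 1.20 × 1.20 = 1.44.
- Equal steps that reach +40%: 1.40^(1/3) − 1 = 11.9% each.

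**2. Early rise.** If creatinine is a fraction *d* above baseline at V4, an event at V6 needs 1.40 × (1 + *d*) relative to baseline:
- *d* = 5%: 1.47
- *d* = 10%: 1.54
- *d* = 15%: 1.61

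The size of *d* is an assumption, because the documents give none for dapagliflozin in transplant recipients. The nearest figure is the ten-patient canagliflozin series in Table 1, with a mean eGFR change of −4.3. If creatinine is inversely proportional to eGFR, an assumed starting eGFR of 75 gives 75/70.7 − 1 = 6% and one of 30 gives 30/25.7 − 1 = 17%. Protocol 2.5 describes that series as having eGFR above 60, which points to the lower end.

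**3. Direction.** At V4 the reference is still baseline, so an early rise makes an event easier to reach: with *d* = 10%, a further 1.40/1.10 − 1 = 27% is enough. At V6 and V9 a persisting early rise is in both numerator and denominator and cancels for an insult of equal proportional size.

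**4. Simulation** (400,000 patients per scenario, creatinine limb only). Assumptions: within-patient SD of log creatinine 0.05, 0.08 or 0.12; the early rise, where present, is 10% from V4 to V9 and gone by V10; the stepwise rise is three equal log steps at V4, V6 and V9, held at V10; the one-visit rise falls at random at V4, V6 or V9. Percentage flagged at SD 0.05 / 0.08 / 0.12:

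| Scenario | Previous draw | V3 reference |
|---|---|---|
| Stepwise +50%, no early rise | 0.7 / 11.2 / 35.7 | 93.5 / 87.0 / 82.8 |
| One-visit +40%, no early rise | 49.9 / 50.3 / 53.0 | 50.1 / 50.0 / 50.7 |
| One-visit +40%, early rise 10% | 63.6 / 60.8 / 61.8 | 91.2 / 80.0 / 72.1 |
| No insult, no early rise | 0.0 / 0.6 / 9.3 | 0.0 / 0.5 / 7.4 |
| No insult, early rise 10% | 0.0 / 1.9 / 12.9 | 0.1 / 4.3 / 18.3 |

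For the one-visit +40% rise at SD 0.08, the previous-draw rule flags at V4 27.7% with the early rise and 16.8% without. At V6 or later it flags 33.5% and 33.6%, against 54.5% and 33.5% with the V3 reference.

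**5. Applying the rule.** The visit before V6 is V5 and the visit before V9 is V8, and neither has a blood sample in Table 2. Read literally, there is no reference creatinine at week 6 or week 12. Read as the previous draw, the intervals are 42 − 7 = 35 days and 82 − 42 = 40 days, using Table 2's study days.

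**The case against.** The strongest reply has four parts.

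First, hospitalisation for AKI is an independent route, so it would be wrong to say that AKI is judged only against the previous visit or that stepwise rises can never count. This stands, and the point is limited to the creatinine limb.

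Second, a reader might infer that the moving reference favours dapagliflozin, since an early dip in GFR raises the week-1 creatinine. The documents do not support that. An early rise counts against the drug at week 1 and cancels afterwards for an equal proportional insult. It is the baseline reference that flags more events when an early rise is present. Nor does the protocol commit itself to a dip here: Protocol 2.3 describes other trials, while Protocol 3.3 expects dapagliflozin to lower several markers "while having neutral effects on cardiac and renal function over the course of the 12-week study period".

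Third, a recent reference is defensible for an acute event. This stands as a reason to keep the definition, although intervals of 35 and 40 days weaken it.

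Fourth, cumulative change is visible elsewhere. The SAP models measured GFR, eGFR, creatinine clearance and plasma creatinine from baseline, and Protocol 10.3 promises a summary of mandated laboratory results. This stands in part. Those models estimate mean changes from V3 to V4 and from V3 to V9. They do not count patients past a threshold, and the week-6 and week-13 creatinine values enter none of them.

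**Conclusion.** The point holds for the creatinine limb. With no baseline-referenced criterion, a stepwise rise below 40% per draw is not counted as AKI unless the patient is hospitalised for it, and it may not be recorded as an adverse event. The 2.69-fold example is a boundary case, not a forecast. The more telling figures are the three 11.9% steps that reach +40%, and the simulated 50% stepwise rise flagged in 1–36% of patients under the present rule against 83–94% with the V3 reference. Those percentages rest on the assumed variability and pattern of rise.

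An early rise lifts the later threshold measured from baseline (to +54% if it is 10%), but no net bias towards the drug is claimed. The neutrality after week 1 assumes insults of equal proportional size, and the documents offer nothing firmer on which to settle a direction.

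Separately, the previous-visit reference cannot be applied as written at Visits 6 and 9.

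The consequence is modest. AKI is tabulated without a test in a trial of 52, so no power figure, error rate or primary conclusion changes. What is affected is the completeness of a named safety outcome.

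**What to change.** Keep the definition in Protocol 10.2.3 and its 40% figure. Add to SAP 2.1 a descriptive line: the number of participants in each arm, with denominators, whose serum creatinine is at least 40% above their Visit 3 value at any later draw (Visits 4, 6, 9 and 10). Show it beside the protocol-defined AKI count, with no test.

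Reconcile Protocol 9.1.2, Protocol 10.2.3 and Table 2, so that it is clear whether day 77 is in person and which creatinine value is the reference at Visits 6 and 9.

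The cost is a sentence or two in each document. The samples are already scheduled and no alpha is spent. The downside is that some expected haemodynamic rises will enter the second count, and more of them in an arm with an early rise: at SD 0.08 with no injury, 4.3% are flagged with an assumed 10% early rise against 0.5% without. Showing both counts lets the reader see this.

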10.3 Recording of Adverse Events

• Time Period for Collection of Adverse Events

For this study, SAEs, discontinuations due to AEs (DAEs), AEs of special interest and other AEs will be collected from the time of signing the informed consent and throughout the study, including the run-in and wash-out periods. Information about all adverse events (serious or not) will be recorded in source documents according to good clinical practice, and retained at the investigative sites.

• Follow-up of Unresolved Adverse Events

Any SAEs, DAEs, AE of special interest, or other AEs will be followed by the investigator until resolution or until a clinically stable outcome is reached, or until further follow-up is no longer considered by the investigator to provide clinically meaningful information.

• Variables

The following variables will be collected for each SAE/DAE/AE:

AE (verbatim); The date and time when the AE started and stopped; Intensity; Whether the AE is serious or not; Investigator causality rating against the study drug (yes or no).

Action taken with regard to study drug; AE caused patient's withdrawal from study (yes or no); Outcome.

In addition, the following variables will be collected for SAEs:

Date AE met criteria for a serious AE; Date Investigator became aware of the SAE.

SAE Variables to be collected:

- i. Date of hospitalisation (if applicable).
- ii. Date of discharge (if applicable).
- iii. Probable cause of death (if applicable).
- iv. Date of death (if applicable).
- v. Autopsy performed (if applicable).
- vi. Causality assessment in relation to Study procedure(s).
- vii. Causality assessment in relation to other medication (e.g., concomitant medication, background therapy).

Description of intensity

The intensity of the reported SAEs/DAEs/AE will be assessed according to the following scale:

- \circ Mild (awareness of sign or symptom, but easily tolerated).
- Moderate (discomfort sufficient to cause interference with normal activities).
- Severe (incapacitating, with inability to perform normal activities).

It is important to distinguish between serious and severe AEs. Severity is a measure of intensity whereas seriousness is defined by the criteria above. An AE of severe intensity need not necessarily be considered serious. For example, nausea that persists for several hours may be considered

severe nausea, but not a SAE unless it meets the criteria shown in above. On the other hand, a stroke that results in only a limited degree of disability may be considered a mild stroke but would be a SAE when it satisfies the above criteria.

• Causality Collection

The Investigator will assess causal relationship between Investigational Product and each SAE/DAE, and answer 'yes' or 'no' to the question 'Do you consider that there is a reasonable possibility that the event may have been caused by the investigational product?'

• Adverse Events Based on Signs and Symptoms

All SAEs/DAEs/AE spontaneously reported by the patient or reported in response to the open question from the study personnel: 'Have you had any health problems since the previous visit/you were last asked?' or revealed by observation will be collected and recorded in the eCRF. When collecting SAEs/DAEs/AEs, the recording of diagnoses is preferred (when possible) to recording a list of signs and symptoms. However, if a diagnosis is known and there are other signs or symptoms that are not generally part of the diagnosis, the diagnosis and each sign or symptom will be recorded separately.

• Adverse Events Based on Examinations and Tests

The results from protocol mandated laboratory tests and vital signs will be summarised in the clinical study report. Deterioration as compared to baseline in protocol-mandated laboratory values, or vital signs should therefore only be reported as AEs if they fulfil any of the SAE criteria, are the reason for discontinuation of study treatment, or fulfil criteria of AEs of special interest. If deterioration in a laboratory value/vital sign is associated with clinical signs and symptoms, the sign or symptom will be reported as an SAE/DAE or AE and the associated laboratory result/vital sign will be considered as additional information. Wherever possible the reporting Investigator uses the clinical, rather than the laboratory term (e.g., anaemia versus low haemoglobin value). In the absence of clinical signs or symptoms, clinically relevant deteriorations in non-mandated parameters should be reported as AE(s).

Any new or aggravated clinically relevant abnormal medical finding at a physical examination as compared with the baseline assessment will be reported as an AE.

